6.6 Dose modification

Dose modification is not applicable in this study.

6.7 Criteria for study hold or dosing stoppage

UCB reserves the right to temporarily suspend or prematurely discontinue this study either at a single site, multiple sites, or at all sites at any time for reasons including, but not limited to, safety or ethical issues, inaccurate or incomplete data recording, noncompliance, or unsatisfactory enrollment with respect to quality or quantity. See Section 9.7 for details on interim analyses to be evaluated by the DMC (ie, study may be stopped for futility but not for superior efficacy).

If the study is prematurely terminated or suspended, UCB (or its representative) will inform the Investigators/institutions and the regulatory authority(ies) of the termination or suspension and the reason(s) for the termination or suspension, in accordance with applicable regulatory requirement(s). The Institutional Review Board (IRB)/ Independent Ethics Committee (IEC) should also be informed and provided with reason(s) for the termination or suspension by the Sponsor or by the Investigator/institution, as specified by the applicable regulatory requirement(s). In addition, arrangements will be made for the return or destruction of all unused IMP and other material in accordance with UCB procedures for the study.

Detailed procedures for reporting SAEs and other safety events which may meet study hold criteria are provided in Appendix 8.

6.8 Treatment after the end of the study

Study participants who complete HS0004 will have the option of enrolling in a Phase 3, multicenter, extension study (HS0005).

Study participants who elect not to enroll in HS0005 at Week 48 will be scheduled to have the SFU Visit 20 weeks after the final injection of IMP. During the SFU, if study participants' HS deteriorates, the Investigator may consider standard of care for HS treatment after discussion with the Medical Monitor or UCB study physician. Note that the half-life of bimekizumab must be considered in selection of appropriate HS treatments during the SFU period. All concomitant medications and HS interventions administered during the SFU will be recorded on the appropriate eCRF pages.

7 DISCONTINUATION OF STUDY MEDICATION AND PARTICIPANT DISCONTINUATION/WITHDRAWAL

7.1 Discontinuation of study medication

Study medication will be stopped if the study participant develops a medical condition, adverse event (AE), or laboratory abnormality that, in the opinion of the Investigator, compromises the safety of the study participant or his or her ability to continue participation in the study. Study participants who are discontinued from IMP should be encouraged by the Investigator to return for all scheduled visits through Week 48, and the SFU Visit (if the Week 48 Visit is ≥ 20 weeks after the final dose of IMP, the SFU Visit is not required). Any study participant who discontinues IMP but continues in the study should be discussed with the Medical Monitor or UCB study physician.

In all cases the study participant should be followed until the condition has resolved as agreed by the Investigator and the UCB study physician. Investigators should contact the Medical Monitor and/or UCB study physician, in advance whenever possible, to discuss the withdrawal of a study participant.

Study medication will be stopped if the study participant has a confirmed positive coronavirus disease 2019 (COVID-19) test result or a suspected COVID-19 infection. Study medication can be resumed after the participant's recovery from COVID-19, based on the Investigator's clinical judgement. All such cases must be discussed with the Medical Monitor or UCB study physician.

7.1.1 Study participant does not achieve partial response

If a study participant does not achieve a partial response (defined as a $\geq 25\%$ reduction in AN count from Baseline [Week 0]) at any visit from Week 32 to 46, the Investigator should contact the Medical Monitor to discuss whether the study participant should continue on study.

7.1.2 Potential drug-induced liver injury IMP discontinuation criteria

Study participants with potential drug-induced liver injury (PDILI) must be assessed to determine if IMP must be discontinued. In addition, all concomitant medications and herbal supplements that are not medically necessary should also be discontinued.

7.1.2.1 PDILI Discontinuation Criteria

The PDILI criteria below require immediate discontinuation of IMP for study participants with either of the following (see Section 10.6.2.1):

- ALT or AST $\geq 8 \times$ ULN
- ALT or AST $\geq 3 \times$ ULN and coexisting total bilirubin $\geq 2 \times$ ULN

Similarly, the PDILI criterion below requires immediate discontinuation of IMP for:

- Study participants with ALT or AST $\geq 3 \times$ ULN who exhibit temporally associated symptoms of hepatitis or hypersensitivity. Hepatitis symptoms include fatigue, nausea, vomiting, right upper quadrant pain or tenderness. Hypersensitivity symptoms include fever (without clear alternative cause), rash, or eosinophilia (ie, $>5\%$).

If a nondrug-related cause for the symptoms can be confirmed, these study participants may resume IMP administration after discussion with the Medical Monitor and/or UCB study physician, but only when the requirements for rechallenge with IMP as provided in Section 10.6.2.1 are followed.

The PDILI criterion below allows for study participants to continue on IMP at the discretion of the Investigator.

- Study participants with ALT or AST $\geq 5 \times \text{ULN}$ and $< 8 \times \text{ULN}$, total bilirubin $< 2 \times \text{ULN}$, and no eosinophilia (ie, $\leq 5\%$), with no fever, rash, or symptoms of hepatitis (eg, fatigue, nausea, vomiting, right upper quadrant pain or tenderness).

Evaluation of PDILI must be initiated as described in Section 10.6 (Appendix 6) with repeat tests performed in 2 weeks. Upon retest, if ALT or AST values have reduced to $< 5 \times \text{ULN}$, the study participant can continue with the study. However, if ALT or AST remains $\geq 5 \times \text{ULN}$ and $< 8 \times \text{ULN}$ after retest, IMP should be temporarily withheld and study participant should undergo a repeat test in 2 weeks. If ALT or AST values remain $\geq 5 \times \text{ULN}$ even after the second retest, then the study participant should be permanently withdrawn from IMP and should be followed for possible PDILI.

If study participants are unable to comply with the applicable monitoring schedule, IMP must be discontinued immediately.

Investigators should attempt to obtain information on study participants in the case of IMP discontinuation to complete the final evaluation. Study participants with PDILI should not be withdrawn from the study until investigation and monitoring are complete. All results of these evaluations and observations, as well as the reason(s) for IMP discontinuation and study participant withdrawal (if applicable), must be recorded in the source documents. The eCRF must document the primary reason for IMP discontinuation.

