≥5×ULN (and ≥2× Baseline) and <8×ULN	<2×ULN	No	Discussion with Medical Monitor required. Consider need for hepatology consult if there is no evidence of resolution (see Follow-up requirements). ^c	Further investigation – immediate IMP discontinuation not required (see Section 10.6.2). IMP discontinuation required if any of the following occur: 
 • Subject cannot comply with monitoring schedule. • Liver chemistry values continue to increase • Liver chemistry values remain ≥5×ULN (and ≥2× baseline) after 4 weeks of monitoring without evidence of resolution 	Essential: Every attempt must be made to have repeat liver chemistry values and additional testing completed within 48 hours at the site with HCP (see Section 10.6.3).	Monitoring of liver chemistry values at least twice per week for 2 weeks. ^c 
 • Immediate IMP discontinuation required if liver chemistry values continue to increase. After 2 weeks of monitoring liver chemistry values: 
 • ALT or AST remains ≥5×ULN <8×ULN, IMP should be temporarily withheld and subject should undergo repeat test in 2 weeks. Continue IMP if ALT or AST values <5×ULN; continue to monitor at least twice per week until values normalize, stabilize, or return to within baseline values. If ALT or AST remains ≥5×ULN after second retest, immediate IMP discontinuation required. Continue to monitor until values normalize, stabilize, or return to within baseline values. ^d

Table 10–1: Required investigations and follow-up for PDILI

Laboratory value			Immediate		Follow up	
ALT or AST	Total bilirubin	Symptoms ^a of hepatitis or hypersensitivity	Consultation requirements	Actions	Testing	Evaluation

ALP=alkaline phosphatase; ALT=alanine aminotransferase; ASAP=as soon as possible; AST=aspartate aminotransferase; HCP=healthcare practitioner; IMP=investigational medicinal product; NA=not applicable; PDILI=potential drug induced liver injury; ULN=upper limit of normal

^a Hepatitis symptoms include fatigue, nausea, vomiting, and right upper quadrant pain or tenderness; hypersensitivity symptoms include eosinophilia (>5%), rash, and fever (without clear alternative cause).

^b If the subject also has $\geq 2 \times$ ULN ALP, the possibility of an indication of biliary obstruction should be discussed with the Medical Monitor.

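### For ALT or AST of 5 to <8×ULN, Section 7.1.2.1 and Table 10-1 give different actions on rising values and different retest times

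*Protocol*

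**What the plan says.** **Section 7.1.2.1**, for ALT or AST from 5 to below 8×ULN with bilirubin below 2×ULN and none of the listed symptoms, opens with: "The PDILI criterion below allows for study participants to continue on IMP at the discretion of the Investigator". It then states: "Evaluation of PDILI must be initiated as described in Section 10.6 (Appendix 6) with repeat tests performed in 2 weeks". If the retest is below 5×ULN, the participant continues. If it is still 5 to below 8×ULN: "IMP should be temporarily withheld and study participant should undergo a repeat test in 2 weeks". If it is still at least 5×ULN after that second retest, IMP is permanently withdrawn.

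**Table 10-1 (Section 10.6)** has a row for "≥5×ULN (and ≥2× Baseline) and <8×ULN" with bilirubin below 2×ULN and no symptoms. On retesting it says: "Every attempt must be made to have repeat liver chemistry values and additional testing completed within 48 hours at the site with HCP". Liver values are then monitored at least twice per week for 2 weeks. On a rise it says: "Immediate IMP discontinuation required if liver chemistry values continue to increase". The row's Actions column also lists a continuing increase among the reasons to discontinue IMP. At 2 weeks and at the second retest, the Evaluation column follows the same sequence as Section 7.1.2.1.

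**The concern.** Both places tell a site what to do with the same laboratory result, and they do not tell it the same thing. The most important difference is the rising value. One place requires IMP to be discontinued at once. The other is silent on a rise below 8×ULN, and its next step is a temporary hold.

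That difference has consequences. Section 10.6 makes a stop for PDILI permanent unless an alternative diagnosis fully explains the findings, and Section 10.6.2.1 sets strict conditions for rechallenge. Section 10.6 ties that permanence to stops described in Section 7.1.2.1, where the rising-value stop does not appear, so it is also unclear whether permanence applies to it.

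Section 7.1.2.1 further requires IMP to stop if the participant cannot keep to the applicable monitoring schedule. If the schedule is ambiguous, so is that stop. Hepatic events and PDILI are a prespecified safety topic (Section 8.3.7), and sites could in good faith manage the same participant differently.

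**Working it through.** The protocol gives no figure to reproduce. The check sets the two texts side by side for ALT/AST of 5 to <8×ULN, bilirubin <2×ULN and no symptoms.

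| Item | Section 7.1.2.1 | Table 10-1 |
|---|---|---|
| First retest | 2 weeks | Within 48 hours |
| Tests in first 2 weeks | 1 | At least 2 per week × 2 weeks = 4 |
| Value rising, still <8×ULN | No rule; hold at the 2-week retest | Immediate discontinuation |
| Baseline condition | None | At least 2× Baseline |
| Still 5 to <8×ULN at 2 weeks | Hold, retest in 2 weeks | Same |
| Still ≥5×ULN after second retest (2 + 2 = 4 weeks) | Permanent withdrawal of IMP | Discontinuation (Evaluation column) |

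**Rising values.** Take 5.5×ULN rising to 7.5×ULN. Under Section 7.1.2.1 the 2-week retest gives a temporary hold and another test 2 weeks later. Under Table 10-1 a continuing increase means immediate discontinuation. The example assumes that this rise meets the table's trigger, since the table does not say how many results make a continuing increase.

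**Retest timing.** 14 days against about 2 days.

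**Baseline condition.** Let v be the current value and B the Baseline value, both in multiples of ULN. The table's extra condition is v ≥ 2B. With v ≥ 5 it can fail only if B > 5/2 = 2.5. Exclusion criterion 29 removes participants at or above 3×ULN at Screening. If Baseline is also below 3, then 2B < 6, so the two texts differ only for v from 5 to below 6 and B above 2.5 and below 3. Such a participant is covered by Section 7.1.2.1 but falls outside this row of the table.

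**Which text governs.** Section 7.1.2.1 refers to Section 10.6 for the evaluation, and Section 7.1.2.1.1 refers follow-up monitoring to Table 10-1. For the decision to discontinue, the references run the other way: the opening of Section 10.6 and criterion 5a in Section 7.2 both refer to Section 7.1.2. Section 10.6.2 cites Section 7.1.2 and Table 10-1 together, with no order of precedence.

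**A small mismatch inside the table.** Its Actions column words the late stop as "after 4 weeks of monitoring without evidence of resolution" and attaches the 2× Baseline condition. Its Evaluation column and Section 7.1.2.1 do neither.

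**The case against.** The best defence is that the two places are summary and detail. The sentence giving the 2-week interval itself sends the site to Appendix 6, and Section 7.1.2.1.1, directly after it, sends monitoring to Table 10-1. The table has its own decision point after 2 weeks, with nearly the same sequence. A careful site can therefore read 2 weeks as the decision point, with the 48-hour and twice-weekly tests falling inside that window. This is a fair reading and weakens the timing point. But the text does not say so, because it attaches the 2-week interval to the repeat tests themselves.

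On rising values, the defence is that Section 7.1.2.1 omits the table's stop without contradicting it. That is true of the wording, since it never says that rising values may be ignored. The actions still differ, and the references on stopping IMP lead back to the section that lacks the rule. A footnote to Table 10-1 allows an agreed alternative monitoring schedule; it does not address the stop on rising values.

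A reader might infer that a site using Section 7.1.2.1 would act on nothing but the 2-week result and could dose through any rise. The protocol does not support that. The same section requires an immediate stop at 8×ULN or above, at 3×ULN or above with bilirubin at least 2×ULN, and at 3×ULN or above with symptoms. Section 10.6.1 requires the Medical Monitor or study physician to be notified of PDILI events within 24 hours. The exposure is limited to asymptomatic rises below 8×ULN with bilirubin below 2×ULN.

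**Conclusion.** The inconsistency is real and is in the current text. The conflict over rising values carries the point, because the same result can mean a temporary hold or immediate discontinuation. The retest difference is second: 14 days against about 2 days as written, less if a site follows every cross-reference. The Baseline condition is minor and, assuming no rise to 3×ULN or above between Screening and Baseline, reaches only the narrow band shown above.

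A reader might go on to infer an effect on the primary endpoint, because Section 9.3.1 counts stopping study treatment for an AE before Week 16 as an intercurrent event, hence as non-response. The protocol does not support claiming one. It gives no expected number of participants reaching 5 to <8×ULN before Week 16, and Section 2.3 reports few markedly abnormal liver values in HS0001. The point rests on consistent safety management across sites.

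**What to change.** Reconcile Section 7.1.2.1 and the matching row of Table 10-1 into one rule covering the action on rising values, the timing and frequency of retests, and whether the Baseline condition applies. Make the table's Actions and Evaluation columns agree on the late stop. State the rule once, and have the other place refer to it without an interval of its own. Make clear whether the permanence rule in Section 10.6 covers a stop for rising values. The clinical content is the sponsor's choice.

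The cost is protocol wording and a clarification letter to sites.

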7.1.2.1.1 Follow-up evaluation

Potential drug-induced liver injury events require follow-up monitoring as described in Table 10–1. Monitoring should continue until liver chemistry values normalize, stabilize, or return to Baseline. Determination of stabilization is at the discretion of the Investigator in consultation with the hepatologist (as applicable) and UCB study physician, as needed.

7.1.3 Treatment interruptions

If a study participant is found to be persistently noncompliant (for example, missing 2 or more of the doses in the Initial Treatment Period or 3 or more doses during Maintenance Treatment Period) the Sponsor, in conjunction with the Investigator, will make a decision as to whether the study participant should be withdrawn from the study.

Note: Doses of IMP that were missed due to a reasonable interfering AE that does not allow administration of IMP due to safety reasons will not be considered for the evaluation of study participant discontinuation. Evaluation of the reasonability of the AE should be discussed immediately with the Medical Monitor.

Any participant who develops a clinically important infection or recurrent infections not responsive to standard therapy during the study must discontinue IMP until resolution of the

infection. The Investigator should use clinical judgement in deciding whether the participant should restart IMP and contact the Medical Monitor and UCB study physician to confirm the participant's suitability for continued participation in the study.

7.2 Participant discontinuation/withdrawal from the study

Note: For female study participants, please see Section 8.3.5 for pregnancy that occurs during the study as evidenced by a positive pregnancy test.

Study participants are free to withdraw from the study at any time, without prejudice to their continued care.

A study participant may withdraw from the study at any time at his or her own request, or may be withdrawn at any time at the discretion of the Investigator for safety, behavioral, compliance, or administrative reasons.

If the study participant withdraws consent for disclosure of future information, the Sponsor may retain and continue to use any data collected before such a withdrawal of consent.

If a study participant withdraws from the study, he or she may request destruction of any samples taken and not tested, and the Investigator must document this in the site study records.

See the Schedule of Activities (Table 1–1) for data to be collected at the time of study discontinuation and follow-up and for any further evaluations that need to be completed.

If a study participant does not achieve a partial response (defined as a $\geq 25\%$ reduction in AN count from Baseline [Week 0]) at any visit from Week 32 to 46, the Investigator should contact the Medical Monitor to discuss whether the study participant should continue on study.

Study participants will be withdrawn from the study, after being encouraged to complete the Premature End of Treatment (PEOT) and the SFU Visit if either of the following events occur:

1. Study participant withdraws his or her consent.
2. The Sponsor or a regulatory agency requests withdrawal of the study participant.

Study participants should be withdrawn from IMP and encouraged by the Investigator to return for all scheduled visits through Week 48, and the SFU Visit (if the Week 48 Visit is ≥ 20 weeks after the final dose of IMP, the SFU Visit is not required) if any of the following events occur:

1. Study participant develops an illness that would interfere with his or her continued participation.
2. Study participant is noncompliant with the study procedures or medications in the opinion of the Investigator.
3. Study participant takes prohibited concomitant medications as defined in this protocol (Section 6.5.2) that may present a risk to the safety of the participant or the integrity of the study data, in the opinion of the Investigator and/or the Medical Monitor and/or UCB study physician.
4. Study participant requires more than the number of protocol-allowed lesion interventions (see Section 6.5.3.2).

5. Study participant has a clinical laboratory value meeting any of the following criteria:
 - a. Hepatotoxicity as described in Section 7.1.2.
 - b. A laboratory value meeting any of the following criteria:
 - Absolute neutrophil count $<1.0 \times 10^3/\mu\text{L}$
 - Absolute lymphocyte count $<200 \text{ cells}/\mu\text{L}$

Study participants may remain on IMP if the result is transient. A retest is required within 1 to 2 weeks at a scheduled or unscheduled visit. If the repeat absolute neutrophil count or absolute lymphocyte count is still below the allowable values, the participant must be discontinued from the IMP. If the repeat absolute neutrophil count or absolute lymphocyte count is above the allowable values, the participant may continue to receive IMP.

6. There is confirmation of a pregnancy during the study, as evidenced by a positive pregnancy test (see Section 8.3.5 for more information regarding pregnancies).
7. A study participant considered as having either a suspected new LTBI or who develops active TB or an NTM infection during the study (including but not limited to, conversion demonstrated by interferon gamma release assay [IGRA] or other diagnostic means) must be immediately discontinued from IMP.
 - The study participant must immediately be permanently withdrawn from the study if further examinations result in a diagnosis of the following:
 - active TB or
 - an NTM infection, or
 - latent TB infection and study participant does not initiate TB prophylactic therapy, prematurely discontinues TB prophylactic therapy, or, in the opinion of the Investigator or Sponsor, is noncompliant with TB prophylactic therapy.

The PEOT Visit must be scheduled as soon as possible, but not later than the next regular visit.

- If the study participant is diagnosed with LTBI during the study and desires to continue in the study, he or she must immediately discontinue IMP and start TB prophylactic therapy. After at least 4 weeks of TB prophylaxis, the IMP can be restarted after discussion with the UCB study physician regarding results of laboratory assessments, physical examination, and TB questionnaire. The full course of TB prophylaxis treatment will be completed during the study.

Confirmed active TB is an SAE and must be captured on an SAE Report Form and provided to the Sponsor in accordance with SAE reporting requirements. As with all SAEs, periodic follow-up reports should be completed as per protocol requirements until such time as the TB infection resolves.

Additional information on TB policies is provided in Section 8.2.6.

8. Study participants with newly diagnosed IBD or with IBD flares during the study must:

- Be referred, as appropriate, to a healthcare professional treating IBD, such as a gastroenterologist
- Discontinue IMP and be followed-up until resolution of active IBD symptoms

If IBD flares increase in severity or frequency during the study, the Investigator should use clinical judgement in deciding whether the study participant should continue on IMP and contact the Medical Monitor and UCB study physician to confirm the study participant's suitability for continued participation in the study.

- 9 Study participants must be referred immediately to a mental healthcare professional and may be withdrawn from the study based upon the Investigator's judgment of benefit/risk for:
- Active suicidal ideation as indicated by a positive response ("Yes") to Question 4 of the "Since Last Visit" version of the eC-SSRS
 - Moderately severe major depression as indicated by a PHQ-9 score of 15 to 19 if this represents an increase of at least 3 points compared to the last visit

The mental health consultation must be recorded in the study participant's source documentation.

10. Study participants must be referred immediately to a mental healthcare professional and must be withdrawn from the study in case of:

- Active suicidal ideation as indicated by a positive response ("Yes") to Question 5 of the "Since Last Visit" version of the eC-SSRS.
- Any suicidal behavior since last visit.
- Severe major depression as indicated by a PHQ-9 score ≥ 20 .

The mental health consultation must be recorded in the study participant's source documentation.

Investigators should contact the Medical Monitor in advance, whenever possible, to discuss the withdrawal of a study participant from IMP or from the study.

Study participants withdrawing from the study who are not continuing for all scheduled visits through Week 48, will undergo the PEOT Visit and the SFU Visit 20 weeks after their final dose of IMP, as applicable.

The eCRF must document the primary reason for withdrawal or discontinuation.

Investigators should contact the Medical Monitor and/or UCB study physician, whenever possible, to discuss the withdrawal of a study participant in advance.

Withdrawn participants will not be replaced.

